9.1.7 Dyspareunia

9.1.7.1 The mean daily NRS score for worst dyspareunia

For each cycle, the mean daily NRS score for worst dyspareunia is calculated as the mean of the worst pain during or after sexual intercourse (question 4) for that cycle. There are no minimal requirements on the number of times question 4 is answer for the mean to be calculated.

9.1.7.2 Frequency of avoiding sexual intercourse

For the analysis of frequency of avoiding sexual intercourse, two variables are needed, firstly the number of days during that cycle that the subject avoids sexual intercourse because of expected pain (that is how many times the subject answers yes to question 3) is needed. Secondly the number of days during that cycle that the subject does not avoid having sexual intercourse because of expected pain (that is how many times the subject answers the subject answers yes to question 3) is needed.

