### The questions to be answered are

2. Did you have sexual intercourse in the past 24 hours?

- 🗆 No
- □ Yes

If the subject did not have sexual intercourse in the past 24 hours:

3. Did you **avoid** sexual intercourse in the past 24 hours because of expected endometriosis-related pain?

 $\Box \operatorname{No} \\ \Box \operatorname{Yes} \\$ 

If the subject had sexual intercourse in the past 24 hours:

4. Pleas	e rate yo	ur worst	pain dur	ing or aft	er sexual	intercou	urse in the	e past 24	hours.	
0	1	2	3	4	5	6	7	8	9	10
No										Worst
pain										imaginable
										pain

Quinagolide, FE 999051	Trial Code: 000165	Date: 29 May 2020
Vaginal Delivery System		E-Study Protocol-20036; Ver.6.0
Clinical Trial Protocol		Supersedes: 5.0
		Page 74 of 130

The mean of the NRS scores obtained for dyspareunia on the days with sexual intercourse and the frequency of avoiding sexual intercourse during the two run-in menstrual cycles (cycles -2 and -1) will be considered baseline of the respective endpoint.

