### 9.6.3 Secondary and Exploratory Endpoints

Secondary endpoints of change from baseline in the mean daily NRS score for the worst dysmenorrhea and for the worst non-menstrual pelvic pain at cycle 4 will be analyzed longitudinally and similarly to the primary endpoint, with the focus on estimating the treatment effect at cycle 4. Sensitivity analyses will not be performed for secondary endpoints.

Secondary endpoints over all 4 cycles or for cycles pre-specified in endpoints will be analyzed longitudinally as follows:

- Continuous endpoints will be analyzed by repeated measures ANCOVA
- Responder status endpoints will be analyzed using repeated measures logistic regression using the generalized estimating equation (GEE) approach for binary data with logit link function and by analyzing the time to event of first response using the proportional odds regression model
- Count data relative to particular cycle days (e.g. number of days of avoiding sexual intercourse relative to the total days of either having sexual intercourse or avoiding it

due to endometriosis-related pain) will be analyzed using repeated measures negativebinomial regression using the GEE approach for count data with log link function using the appropriate off-set

These models will include treatment, cycle and treatment by cycle interaction as independent factors and the respective baseline by cycle interaction (as applicable) and the percentage of days on rescue analgesics by type at baseline as covariates. The error-covariance matrix will be unstructured. The possible dependence of the treatment effect on these covariates will be additionally investigated by testing for respective treatment interactions.

The analysis will focus on adjusted treatment contrasts versus placebo during cycles 1-4. Table 9-2 summarizes the respective analyses for all defined secondary and exploratory endpoints.

Table 9-2	Analyses of Se	econdary and Ex	ploratory Endpoints

Endpoint	Analysis Method				Cycles		
	Repeated measures ANCOVA (focusing on cycle 4) X	Repeated measures ANCOVA	Logistic regress- ion (GEE)	Negative Binomial regression (GEE)			
Changes in the mean daily NRS scores for the worst dysmenorrhea and for the worst non-menstrual pelvic pain at cycle 4					4		
Changes in the mean daily NRS scores for the worst endometriosis-related pain over 4 menstrual cycles		Х			1-4		

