9.1 Transformation of daily e-Diary data

Subjects will be ask to fill in the daily e-Diary every day from visit 1 to end-of-trial visit. Every night between 8 pm and 2 am the subject should answer the following question:

Instructions and the question to be answered are:

Please think about the **worst** endometriosis-related pain you experienced in the past 24 hours and rate it on a scale from 0 to 10 where 0 is 'no pain' and 10 is 'worst imaginable pain'. Please do not include pain from sexual intercourse.

1. Please rate your **worst** endometriosis-related pain in the past 24 hours (including pelvic pain, abdominal pain, or lower back pain, whichever is the worst).

` D		¹ □ [′]			Í			Í 🗆		
0	1	2	3	4	5	6	7	8	9	10
No										Worst
pain										imaginable
										pain

2. Did you have sexual intercourse in the past 24 hours?

🗆 No

□ Yes

If the subject did not have sexual intercourse in the past 24 hours:

3. Did you **avoid** sexual intercourse in the past 24 hours because of expected endometriosis-related pain?

 \Box No \Box Yes

If the subject had sexual intercourse in the past 24 hours:

4. Pleas	e rate y	our wor	st pain	during o	r after s	exual in	tercours	e in the	past 24	hours.
0	1	2	3	4	5	6	7	8	9	10
No										Worst
pain										imaginable
										pain

5. How did your endometriosis-related pain limit your sitting, standing and walking in the past 24 hours?

Statistical Analys Quinagolide FE 999051 trial 0	is Plan 00165			V 31 CON	ersion: 1 MAY202 FIDENT	0 22 TIAL				FERRING PHARMACEUTICALS Page 25 (44)
□ 0 No limitations on activities	□ 1	□ 2	□ 3	□ 4	□ 5	6	□ 7	8	□ 9	□ 10 Unable to do activities
6. How did y such as doing □	our en g chore	dometri s, launc	osis-rel lry, coo □	ated pai king, w	in limit ashing o	your da lishes, c	ily activ or cleani □	ities ard ng in th □	ound th	e house, 24 hours? □
0 No limitations on activities	1	2	3	4	5	6	7	8	9	10 Unable to do activities
7. How did v	our en	dometri	osis-rel	ated pai	n limit	vour wo	ork/scho	ol in th	e past 2	4 hours?
□ Not appli □ 0 No limitations on activities	cable,≓ □ 1	no work	c or sch	ool in th	the past 2 \Box 5	24 hours	s. □ 7	∑ m m □ 8	9	□ 10 Unable to do activities
8. How did v	our en	dometri	osis-rel	ated pai	n limit	vour so	cial activ	vities w	rith fam	ilv or
friends in the ☐ 0 No limitations on activities	past 2 □ 1	4 hours □ 2	? □ 3	□ 4	□ 5	6	□ 7	8	9	10 10 Unable to do activities

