9.3 General Considerations

All efficacy endpoints will be summarised by treatment using descriptive statistics. Categorical data will be summarised using numbers and percentages (n and % of all observed) in addition to the sum 'All', the percentages are based on the total number of subjects with a corresponding assessment in the analysis set. Continuous data will be presented, using the number of subjects (n), mean and standard deviation, median, 25th percentile, 75th percentile, minimum, and maximum. The primary endpoint will be summarized using both the ITT population and the PP population, all other endpoints will be summarized using only the ITT population.

As the trial has been prematurely discontinued, it has been decided, due to the low number of subjects, that no statistical analysis will be performed, see section 1 and 12.

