9.3.1 Efficacy and exploratory endpoints

For the primary endpoint, each of the secondary, and each of the exploratory endpoints mentioned in Table 9-1 the absolute value at baseline and the absolute value at cycle 1 to 4 (if appropriate), and the change from baseline at cycles 1 to 4 (if appropriate) will be summarised by treatment.

Table 9-1 Efficacy and Exploratory Endpoints

Endpoint
Changes in the mean daily NRS scores for the worst endometriosis-related pain at cycle 4
Changes in the mean daily NRS scores for the worst endometriosis-related pain over 8 menstrual cycles
Changes in the mean daily NRS scores for the worst dysmenorrhea and for the worst non-menstrual pelvic
pain over 8 menstrual cycles
Changes in the mean daily NRS scores for the worst dyspareunia on days with sexual intercourse over
8 menstrual cycles
Frequency of avoiding sexual intercourse due to expected pain over 8 menstrual cycles
Changes in the mean daily NRS scores for the worst impact of endometriosis-related pain on the subject's
ability to function over 8 menstrual cycles
Changes in the mean weekly scores of the EHP-30 pain impact domain over 8 menstrual cycles
Changes in vaginal bleeding pattern over 8 menstrual cycles
Percentage of days with mild and/or strong rescue analgesics used over 8 menstrual cycles
Total and average doses of mild and/or strong rescue analgesics used over 8 menstrual cycles
Responder rate assessed as ≥30%, ≥50% and ≥70% reduction from the baseline in mean daily NRS scores
for the worst endometriosis-related pain, dysmenorrhea, non-menstrual pelvic pain and for the worst
endometriosis-related pain impact over 8 menstrual cycles
Changes in the mean individual and total symptom and sign severity scores of the B&B scale at cycles 4
and 8
Changes in EHP-30 scores over 8 menstrual cycles
Changes in PGIS scores at cycles 4 and 8
PGIC scores at cycles 4 and 8
Serum levels of mid-luteal phase progesterone ^f , estradiol, prolactin, TSH and IGF-1 at cycles 4

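### SAP 9.1.7.2 defines days avoiding intercourse and days not avoiding it by the same diary answer, so the relative frequency in protocol 9.6.3 cannot be derived from it

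*SAP*

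**What the plan says.** SAP section 9.1.7.2 states that two variables are needed for this endpoint. The first is the number of days in the cycle on which the subject "avoids sexual intercourse because of expected pain (that is how many times the subject answers yes to question 3) is needed". The second is the number of days on which she "does not avoid having sexual intercourse because of expected pain (that is how many times the subject answers the subject answers yes to question 3".

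The diary items are reproduced in SAP section 9.1. Question 2 asks whether intercourse took place. Question 3 asks whether it was avoided because of expected endometriosis-related pain, and it appears only under the condition "If the subject did not have sexual intercourse in the past 24 hours".

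Protocol section 9.6.3 describes the count as "number of days of avoiding sexual intercourse relative to the total days of either having sexual intercourse or avoiding it" because of endometriosis-related pain, as an example of count data to be modelled with an off-set. Protocol section 7.2.1.2 sets the baseline: "the frequency of avoiding sexual intercourse during the two run-in menstrual cycles (cycles -2 and -1) will be considered baseline of the respective endpoint".

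The endpoint is still to be reported. SAP section 9.3 says "All efficacy endpoints will be summarised by treatment using descriptive statistics", and Table 9-1 in section 9.3.1 lists "Frequency of avoiding sexual intercourse due to expected pain over 8 menstrual cycles". For the endpoints in that table, section 9.3.1 promises "the absolute value at baseline and the absolute value at cycle 1 to 4 (if appropriate), and the change from baseline", the change also being qualified by where appropriate. Section 12 names the outputs that were dropped, and this one is not among them.

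**The concern.** A yes to question 3 means that the subject did avoid intercourse. The rule for the second variable is therefore the opposite of its label and identical to the rule for the first. No other part of the SAP supplies the missing count.

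The two variables together were meant to give a numerator and a denominator. With the duplicated rule they carry only one piece of information. A relative frequency built from them is constant wherever it is defined, and it is undefined for subjects who never avoided intercourse, who are the best outcomes. A treatment benefit on this endpoint could not show in the table, and a subject who stopped avoiding intercourse would drop out of the summary instead of counting as zero.

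**Working it through.** The documents give no figure to reproduce here and no day counts. The check is algebraic, and all day counts below are assumptions for illustration.

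**Notation, per subject and cycle**
- a = days with yes to question 3 (avoided)
- h = days with yes to question 2 (had intercourse)
- o = days with no to both

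**Formulas**
- Protocol 9.6.3: a/(a + h)
- SAP 9.1.7.2 as written: first variable = a, second variable = a, so the ratio is a/(a + a) = 0.5 when a ≥ 1 and 0/0 when a = 0
- One-word repair, no to question 3: a/(a + o)

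**Assumed 28-day cycles**

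| h | a | o | Protocol a/(a+h) | SAP as written | No to question 3, a/(a+o) |
|---|---|---|---|---|---|
| 6 | 2 | 20 | 2/8 = 0.25 | 0.50 | 2/22 = 0.091 |
| 2 | 6 | 20 | 6/8 = 0.75 | 0.50 | 6/26 = 0.231 |
| 4 | 4 | 20 | 4/8 = 0.50 | 0.50 | 4/24 = 0.167 |
| 0 | 10 | 18 | 10/10 = 1.00 | 0.50 | 10/28 = 0.357 |
| 8 | 0 | 20 | 0/8 = 0 | undefined | 0/20 = 0 |

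The literal rule agrees with the protocol only when a = h.

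**Range.** For a and h each from 1 to 10, the protocol ratio runs from 1/11 = 9% to 10/11 = 91%. The literal rule gives 50% in all 100 combinations and is right in the 10 where the counts are equal. This grid shows the range; it does not estimate the likely error.

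**Change from baseline, two assumed subjects**
- 8 avoided and 2 intercourse days at baseline, 2 and 6 at cycle 4: protocol 8/10 = 80% to 2/8 = 25%, a fall of 55 points. Literal rule: 50% to 50%, no change.
- 4 and 3 at baseline, 0 and 7 at cycle 4: protocol 4/7 = 57% to 0/7 = 0%, a fall of 57 points. Literal rule: 50% to 0/0, so no value at cycle 4.

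**Why the obvious repair fails.** Question 3 is not asked on days with intercourse. Its no answers therefore omit every intercourse day and include days without intercourse for unrelated reasons. This can reverse the order of subjects. With (h, a, o) = (1, 3, 24) the protocol ratio is 3/4 = 75% and the repair gives 3/27 = 11%. With (15, 5, 8) they are 5/20 = 25% and 5/13 = 38%.

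**The case against.** The strongest reply is that this is a visible editing slip with little left to damage. The sentence stutters, its label states the intent, and the protocol names the correct denominator. A programmer would see two identical variables at once. The negative-binomial model that needed the off-set has been cancelled, so the second variable may have no remaining use. The SAP never tells anyone to divide one count by the sum of the two, and the raw count of avoided days, which is correctly defined, could serve as the reported frequency. The tables are also promised only where appropriate. Finally, SAP section 1 takes protocol version 5.0 as the basis for the report, while the protocol at hand is version 6.0.

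Much of this stands as a limit on the consequence. If the raw count alone is tabulated there is no error, and no inferential result depends on the answer. The wording of section 9.6.3 in version 5.0 cannot be checked.

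It does not remove the defect. The contradiction lies inside SAP 9.1.7.2 and does not depend on the protocol version. That section itself says two variables are needed, so it does not present the raw count as enough. Relying on the programmer is unsafe because the simplest correction, changing yes to no, is also wrong. The protocol's ratio is offered as an example, but it is the only relative definition of this endpoint in either document.

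**Conclusion.** The concern holds. SAP 9.1.7.2 gives one rule to two variables that it describes as opposites, and the relative frequency in protocol 9.6.3 cannot be derived from that rule.

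The size depends on a choice the SAP leaves unstated. If the relative frequency is summarised, the literal rule yields 50% or nothing, against a protocol quantity of 9% to 91% over the assumed counts. Change from baseline is then zero for anyone who avoided intercourse at least once in both periods compared. If the raw count is summarised, there is no effect.

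The reach is one descriptively reported secondary endpoint in a trial that was stopped early. The definition of avoided days is sound, the data needed are collected, and the primary endpoint and safety outputs are untouched. The SAP text should still be corrected, because it is the operative derivation rule for an output that remains planned.

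**What to change.** In SAP 9.1.7.2, replace the second definition with the number of days in the cycle on which question 2 is answered yes. Do not use no answers to question 3.

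State what will be summarised: per cycle, question 3 yes days divided by the sum of question 2 yes days and question 3 yes days. The value is 0 when intercourse occurred and none was avoided, and missing only when both counts are 0. Apply the same rule to the run-in baseline. If the sponsor intends to report only the raw count of avoided days, the SAP should say so and drop the second variable.

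The cost is a short SAP edit and about one line of code. Both questions are already in the daily e-Diary.

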9.1.8 Vaginal bleeding pattern

The vaginal bleeding pattern is evaluated as the number of days per cycle with no bleeding, spotting, light bleeding, moderate bleeding and heavy bleeding days, respectively. Additionally the duration of menstrual and non-menstrual period, and the number of bleeding days during the non-menstrual period, will be calculated.

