# 3.6.2 Selection of Endpoints

The primary endpoint of the present trial is the change in the mean daily NRS score for the worst endometriosis-related pain compared to placebo at cycle 4. Endometriosis-related pain is assessed as pain located in the abdominal-pelvic area and in the lower back area, which is the pain most often complained by endometriosis patients. It is considered appropriate to use a single "endometriosis-related pain" endpoint as the primary endpoint in this first trial investigating the efficacy of quinagolide in endometriosis patients. The major concern for using a summed score instead of two separate scores with one each for dysmenorrhea and non-menstrual pelvic pain is that the treatment effect of some hormonal drugs is driven by amenorrhea or oligomenorrhea, which can make a summed score unrepresentative of the true extent of improvement. However, quinagolide does not affect ovarian function and thereby does not appear to modify the vaginal bleeding pattern. It is therefore reasonable to believe that the treatment effect of quinagolide will not be driven by amenorrhea or oligomenorrhea and can be adequately measured by a single score for "endometriosis-related pain" as the primary endpoint in the present trial.

Subjects will be instructed to score the endometriosis-related pain at its worst during the preceding 24 hours every day before bedtime. Since pain assessment relies on memory, a short recall period of 24 hours, a response based on the worst experience during the day and standardized timing of assessment every night is usually preferable and is in line with clinical experts' and Food and Drug Administration (FDA)'s recommendations. By asking subjects about their worst

Quinagolide, FE 999051 Vaginal Delivery System Clinical Trial Protocol

endometriosis-related pain at the end of every day, the scoring has accounted for the worst pain occurring before any potential use of analgesics and has ensured a consistent recall period of 24 hours. Self-reporting of pain is considered to be the gold standard of chronic pain assessment, because it reflects the inherently subjective nature of pain. The validated 11-point NRS widely used in clinical trials on chronic pain including endometriosis-related pain is selected to quantify the pain intensity.

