  - 12b) At randomization, on the self-administered 11-point NRS, having a mean daily NRS score of ≥4 for the worst endometriosis-related pain during each run-in cycle.
- 13. Completion of the daily e-Diary for at least 80% of the days on average in two run-in cycles, from the day the e-Diary is available at the start of cycle -2 through the day before visit 4 at the end of cycle -1.

- 14. Documentation of a normal cervical cytology or negative results of human papilloma virus (HPV) reflex testing within 24 months of the start of run-in. If atypical squamous cells of undetermined significance were present on prior tests, additional follow-up HPV test results should be negative for high-risk viral subtypes.
- 15. Negative cervical swab for gonorrhea and chlamydia at screening.
- 16. Willing and able to comply with trial procedures, including filling in the e-Diary in English or Spanish, attending scheduled visits and adherence to treatment plan.

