9.1.2 Definition of menstrual period and non-menstrual period

Each cycle is divided into a menstrual period and a non-menstrual period, unless the subject does not have a menstrual bleeding during that cycle (see section 9.1.1), then the entire cycle will be considered non-menstrual.

The first day of menses is based on the start date of menses in the current cycle from the menstruation dates log. If this is missing for any other reason than the subject did not have menses in this cycle, then the first day in that cycle where the subject answers yes to both question 9 and 11 in the e-Diary will be used instead.

The last day of menses is based on the stop date of menses in the current cycle from the menstruation dates log. If the subject does have menses and the stop date is missing then the first day where the subject answers no to either question 9 or 11 in the e-Diary will be used instead. Note that the last day of menses could be in the next cycle relative to the first day of menses.

The menstrual period is defined as the period from the first day of menses to the last day of menses, both included.

The menstrual period of a cycle consists of the bleeding period in the end of the cycle plus the potential bleeding part in the beginning of the cycle. If a subject does not bleed in the end of the cycle, the entire cycles will be considered non-menstrual.

The non-menstrual part of the cycle is defined as the part of the cycle that is not considered the menstrual part.

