9.1.4.1 The mean daily NRS score for worst endometriosis related pain

For each cycle, at least 50% of the NRS scores are required to be observed (including the imputed values as described in subsection 9.1.3) for both the menstrual period and the non-menstrual period (as defined in subsection 9.1.2) to be allowed to calculate the mean daily NRS score for that particular cycle. So if above 50% of the daily NRS scores are missing in either period of that cycle, the mean daily NRS score for worst endometriosis related pain for that cycle should be missing.

As missing daily NRS scores may not be appropriately balanced across menstrual period and non-menstrual period, the mean daily NRS score will be weighted by the lengths of the menstrual period and non-menstrual period to adjust for this potential imbalance.

So the mean daily NRS score is calculated as

$$\frac{l_{mp}\overline{x}_{mp} + l_{non-mp}\overline{x}_{non-mp}}{l_{mp} + l_{non-mp}}$$

Where l_{mp} is the number of days in the menstrual period of the cycle (as defined in subsection 9.1.2), l_{non-mp} is the number of days in the non-menstrual period of the cycle in question (as defined in subsection 9.1.2), \bar{x}_{mp} is the mean daily NRS score based on the observed daily NRS scores (question 1) during the menstrual period (including imputations as described in 9.1.3), and \bar{x}_{non-mp} is the mean daily NRS score (question 1) based on the observed daily NRS scores during the non-menstrual period (including imputations as described in 9.1.3).

If the subject does not have a menstrual period in a cycle the mean daily score is calculated as a simple mean, however if more than 50% of the daily NRS scores are missing the mean daily NRS will be considered missing

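### SAP 9.1.8 scores vaginal bleeding as raw diary-day counts with no denominator or completeness rule, so a change in diary completion reads as a change in bleeding

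*SAP*

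**What the plan says.** SAP 9.1.8 gives the endpoint as five counts: "The vaginal bleeding pattern is evaluated as the number of days per cycle with no bleeding, spotting, light bleeding, moderate bleeding and heavy bleeding". It adds three further measures: "Additionally the duration of menstrual and non-menstrual period, and the number of bleeding days during the non-menstrual period, will be calculated". The five categories come from diary questions 9 and 10. The period durations come mainly from the menstruation dates log. For the end of menses, SAP 9.1.2 says: "The last day of menses is based on the stop date of menses in the current cycle from the menstruation dates log"; the diary is only the fallback.

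SAP 9.3.1 reports absolute values and change from baseline by treatment for cycles 1 to 4. SAP 9.3 summarises this endpoint in the ITT set only and, like SAP 1 and 12, rules out statistical analysis.

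The pain score from the same diary has a completeness rule in SAP 9.1.4.1: "For each cycle, at least 50% of the NRS scores are required to be observed". The rule applies separately to the menstrual and non-menstrual periods, and the score is weighted by period length. The functioning and analgesic measures (SAP 9.1.4.4 and 9.1.5) are calculated only when the pain score is.

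Protocol Table 9-2 assigns bleeding pattern to negative-binomial regression. Protocol 9.6.3 describes that analysis as using the "GEE approach for count data with log link function using the appropriate off-set". Protocol 10.3 bars diary entry once the nightly window has closed. Protocol 7.2.1.4 takes the two run-in cycles as the bleeding baseline without saying whether they are summed or averaged. The SAP gives no bleeding baseline.

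**The concern.** A diary day that was not completed is neither a bleeding day nor a no-bleeding day. It drops out of all five counts, and out of the count of bleeding days in the non-menstrual period. A cycle with few diaries therefore yields small counts, where the pain score for that cycle would be set to missing. If completion differs between run-in and treatment, or between arms, the table shows a difference in bleeding that may be only a difference in diary-keeping. It could equally mask a real increase.

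No other rule covers this. The rule in SAP 5 that removes cycles with more than 20% of diary days missing applies to the per-protocol set, and bleeding is not summarised there.

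The effect of the ring on bleeding pattern is a named secondary objective. Under Protocol 8.3.4, abnormal bleeding is not an adverse event unless it needs intervention or is serious, and SAP 10.2.3.3 refers bleeding to the efficacy outputs. With no model, the descriptive table is the whole result.

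**Working it through.** The documents give no figure for this endpoint, so there is nothing to reproduce. The calculation shows how the definition behaves.

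**Assumptions** (none is given in the documents): a 28-day cycle, 6 true bleeding days all within menses, no true change, and diaries missed at random. Completion is c0 in run-in and c1 in a treatment cycle.

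**Formulas.** Expected recorded days = true days × completion. Apparent change = true days × (c1 − c0). Relative change = c1/c0 − 1, whatever the true number of days.

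| c0 to c1 | Bleeding days recorded | Change | Relative | No-bleeding days recorded (22 true) |
|---|---|---|---|---|
| 90% to 80% | 5.4 to 4.8 | -0.6 | -11% | 19.8 to 17.6 |
| 90% to 60% | 5.4 to 3.6 | -1.8 | -33% | 19.8 to 13.2 |
| 90% to 50% | 5.4 to 3.0 | -2.4 | -44% | 19.8 to 11.0 |
| 80% to 100% | 4.8 to 6.0 | +1.2 | +25% | 17.6 to 22.0 |

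With 4 to 8 true bleeding days, the 90% to 60% case gives 4 × (−0.3) = −1.2 to 8 × (−0.3) = −2.4 days. The last row shows that the sign follows the change in completion.

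**Would a plain percentage of answered days do?** It removes the artefact when diaries are missed evenly, but it has two faults.

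- Cycle length: 6 bleeding days in a fully answered cycle are 6/24 = 25.0% or 6/35 = 17.1%, although the number of bleeding days is the same.
- Diaries missed in menses: if 3 of the 6 menstrual diaries are missed and the other 22 are complete, the share falls from 6/28 = 21% to 3/25 = 12%.

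**Period-weighted version**, in the form of SAP 9.1.4.1. For category k:

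days(k) = L_mp × n_mp(k)/a_mp + L_non × n_non(k)/a_non

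Here L is the period length, a the number of answered days in the period, and n(k) the answered days in category k. For all bleeding categories together:

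- 60% completion at random, in expected numbers: 6 × 3.6/3.6 + 22 × 0/13.2 = 6.0.
- 3 of 6 menstrual diaries missed: 6 × 3/3 + 22 × 0/22 = 6.0. Exactly half the menstrual days are answered, so the cycle still qualifies.
- Fully answered 24-day cycle: 6 × 6/6 + 18 × 0/18 = 6.0. A 35-day cycle: 6 × 6/6 + 29 × 0/29 = 6.0.

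**The case against.** The other side has several good points.

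- **Cycle length.** A reader might infer that every count changes with cycle length and cite no-bleeding days of 24 − 6 = 18 against 35 − 6 = 29, a gap of 11. The spotting to heavy counts need not change with length. The 11 days are the two ends of the run-in eligibility range, not a change from baseline, and a longer bleeding-free interval is itself a feature of bleeding pattern.
- **Direction.** A reader might infer that counts must fall after baseline, because eligibility requires "Completion of the daily e-Diary for at least 80% of the days on average in two run-in cycles" and treatment cycles have no such floor. The documents report no completion rates. Reminders and compliance review continue after randomisation (Protocol 6.1 and 10.3). SAP 9.1.1 also allows diary-free days at the start of cycle -2, which lowers baseline counts and pushes the other way.
- **The protocol's off-set.** A reader might infer that the protocol had solved the problem. It names no off-set for bleeding; its example is avoided intercourse. Only an off-set based on answered days would correct for missed diaries. Protocol 7.2.1.4 also defines bleeding as numbers of days and sets no completeness rule.
- **Other diary variables.** Bleeding is not the only one without a minimum. SAP 9.1.7.1 expressly sets none for dyspareunia, 9.1.7.2 states none for avoided intercourse, and 9.2 accepts one weekly score. Dyspareunia and the weekly score are means, however, so they do not shrink mechanically with missed entries.
- **Primary endpoint.** Protocol 3.6.2 supports the single pain score with the statement that "quinagolide does not affect ovarian function and thereby does not appear to modify the vaginal bleeding pattern". A reader might infer that faulty counts undermine that choice. The statement rests on the Investigator's Brochure, not on this endpoint.
- **Conflict between outputs.** Log-based durations are largely unaffected by missed diaries and measure something different. A divergence is a cross-check, not a contradiction.

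The five counts also sum to the answered days, so a careful analyst could recover a denominator. The SAP does not ask for one. None of these points supplies the missing rule.

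**Conclusion.** The point holds for the five category counts and for bleeding days in the non-menstrual period. As defined, they combine bleeding with diary completion, and no other provision separates the two. In the illustration the false change runs from -0.6 days (-11%) to -2.4 days (-44%) as completion falls from 90% to between 80% and 50%, and it is positive if completion rises.

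Those sizes rest on assumed completion levels and 6 assumed bleeding days. The existence of the effect needs only that completion varies between cycles or arms. The documents do not support a claim about which way the trial's counts will move, or that all counts vary with cycle length.

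The consequence is limited. This is a descriptive secondary endpoint in a trial that was terminated early, and the primary endpoint is unaffected. The change is still worth making, because it alters what is reported and uses data already collected.

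**What to change.** Amend SAP 9.1.8 as follows.

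1. In each cycle, and separately for the menstrual and non-menstrual periods of SAP 9.1.2, take the proportion of answered days (question 9, and question 10 where it applies) in each category. Multiply it by the period length and sum over the two periods, as SAP 9.1.4.1 does for pain.
2. Set the cycle to missing if more than 50% of days are unanswered in either period. Apply the rule to the whole cycle if there is no menstrual period.
3. Score bleeding days in the non-menstrual period the same way: the proportion of answered non-menstrual days with bleeding, times the length of that period, with the same 50% limit.
4. Define baseline as the average of cycles -2 and -1.
5. Show answered diary days and cycle length by cycle and arm next to the bleeding table.

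The cost is a few sentences in the SAP and a changed derivation; no new data are needed. The downside is that cycles with sparse diaries become missing. The scaling also assumes that, within a period, unanswered days resemble answered ones. It does not repair diaries missed selectively on heavier bleeding days, which is a further reason to show the answered days.
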